This is a multi-centre, randomized, phase III trial of best supportive care (BSC) with or without single fraction liver radiation therapy (8 Gy) in patients with end-stage, painful, hepatocellular carcinoma (HCC) or liver metastases.

Stratification:

- Centre
- Type of liver cancer (HCC versus liver metastases)

Primary Endpoint

- Proportion of patients achieving improvement of liver cancer pain/discomfort by ≥ 2 points in pain "intensity at worst" on Brief Pain Inventory (BPI) from baseline to day 30.

Secondary Endpoints

- Proportion of patients experiencing grade ≥ 2 adverse events at day 30 and day 90.
- Proportion of patients alive at day 90.
- Proportion of patients achieving improvement of liver cancer pain/discomfort by ≥ 2 points from baseline to day 30 and day 90 in all BPI pain scores.
- Proportion of patients reporting clinically significant improvement in QoL from baseline to day 30 and day 90 as defined by a ≥ 5 point change in the Functional Assessment of Cancer Therapy (FACT) Hepatobiliary Subscale (FACT-HBS) and Trial Outcome Index (FACT-TOI).
- Proportion of patients achieving a 25% reduction in opioid use at 30 days (employing daily morphine equivalence scale).
- Proportion of patients achieving improvement of liver cancer pain/discomfort by ≥ 2 points in pain "intensity at worst" AND with no increase in opioid use (employing daily morphine equivalence scale) on BPI from baseline to 30 days.

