The natural history of patients with symptomatic liver cancer has not been well researched and there are only a few studies of patient-reported QoL or symptom trials in patients with symptomatic liver cancer. In one study of patients treated with chemotherapy for asymptomatic liver metastases from colorectal carcinoma, there was no improvement in QoL (assessed using EORTC QLQ-C30 and QLQ-LMC21) and more problems with taste, sore mouth, and neuropathy 3 months after chemotherapy [Blazeby 2009]. Although these results are not directly comparable with the HE.1 study cohort who are selected as being unfit for or refractory to systemic agents, it seems unlikely that QoL in patients with more advanced liver metastases or HCC may improve with no interventions or with best supportive care (BSC) alone. There is a paucity of studies that have evaluated the impact of BSC or other treatments on symptoms in patients with end-stage primary or metastatic liver cancer and there is a strong need for prospective evaluation of patient-reported outcomes in such patients treated with novel interventions, such as radiation therapy (RT) or BSC alone.

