The Princess Margaret Cancer Centre study investigated 41 patients with diffuse HCC (21) or liver metastases (20, 50% from a gastrointestinal primary site) who had pain (27), discomfort (6) or other (5) symptoms [*Soliman 2013*]. The use of 8 Gy in one fraction to the whole (or near whole) liver, with an anti-emetic to prevent nausea, resulted in a clinically meaningful improvement in average index symptom intensity assessed using the BPI in 48% (95% CI: 28-68%) of patients one month following RT with no differences between patients with HCC and liver metastases. In patients with pain or abdominal discomfort as their index symptom, pain relief tended to occur within a few days and was sustained with a clinically significant improvement at one month in 55% (95% CI: 32-76%) of patients when evaluating “average” pain/discomfort, and in 59% (95% CI: 36-79%) when evaluating “worst” pain/discomfort in the past 24 hours. The pathophysiology of pain relief is not clearly understood; however objective tumour shrinkage is not required for effective pain relief. There was no reduction in symptoms in patients who had nausea or fatigue as their index symptom. RT treatment was well tolerated. Grade 1 or 2 fatigue, often present at baseline, was common; grade 1 or 2 nausea was seen in 3 patients, and grade 2 gastritis was seen in 1 patient. One patient, who declined anti-emetics prior to RT, developed grade 3 vomiting. There was no other reported toxicity. From a QoL perspective, the benefits were less. Twenty-nine percent (95% CI: 8 – 45%) of patients treated with RT had a significant improvement in FACT-HBS at 30 days and 25% (95% CI: 10- 47%) of patients had significant improvement in FACT- TOI at 30 days. Based on the results of this pilot study, the next logical step is to test, in a multi-institutional randomized study, that RT may lead to a clinically significant hepatic pain reduction and QoL improvement in a greater proportion of patients compared to BSC alone [*Hoyer 2012*].

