Patient-reported QoL will be recorded using the Functional Assessment of Cancer Therapy Hepatobiliary (FACT-Hep) questionnaire, a 45-item instrument consisting of the 27-item cancer specific FACT-General (FACT-G), and a site-specific 18-item hepatobiliary subscale (HBS) (*Heffernan 2002*). The FACT-G consists of four subscales: 1) physical well-being (PWB); 2) social and family well-being; 3) emotional wellbeing; and 4) functional well-being (FWB). The Trial Outcome Index (TOI) is the sum of the PWB, FWB and HBS subscales [*Cella 1993*]. The total FACT-TOI score, FACT-Hep score, FACT-G score and individual scores for each subscale will be scored. FACT was chosen for measuring QoL in these patients since, in the Phase II study, patient compliance was better with FACT versus EORTC [*Soliman 2013*], and FACT was more sensitive to demonstrating benefits in patients than EORTC. FACT QoL has been validated in the use of bone metastases response to radiation therapy and is available in different languages. Changes in QoL are secondary endpoints of this study. The FACT HBS and TOI QoL endpoints are expected to be most likely to discriminate between differences in QoL in the two treatment arms. A change in scores of the FACT-G, FACT-HBS, FACT-TOI and FACT-Hep total score by ≥ 6 , ≥ 5 , ≥ 7 and ≥ 8 respectively are considered clinically significant [*Heffernan 2002*].

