14.0 STATISTICAL CONSIDERATIONS

14.1 Objectives and Design

The primary objective of this multi-centre, randomized, phase III trial is to determine whether a single 8 Gy dose of RT with best supportive care (BSC) would show an improvement of ≥ 2 points in pain "intensity at worst" on the Brief Pain Inventory (BPI) from baseline to day 30 relative to BSC alone in patients with painful liver tumours (either HCC or liver metastases).

Patients will be randomized to receive either a single 8 Gy dose of RT with BSC or BSC alone in a 1:1 ratio using a minimization method after stratification by centre and type of liver cancer (HCC versus liver). Secondary objectives include comparison of proportion of patients experiencing adverse events at day 30 and day 90; proportion of patients alive at day 90; proportion of patients achieving improvement of liver cancer pain/discomfort by ≥ 2 points in pain "intensity at worst" on Brief Pain Inventory (BPI) from baseline to day 30; proportion of patients achieving improvement of liver cancer pain/discomfort by ≥ 2 points from baseline to day 30 and day 90 in other BPI pain scores; proportion of patients reporting clinically significant improvement in QoL from baseline to day 30 and day 90 as defined by a ≥ 5 point change in the Functional Assessment of Cancer Therapy (FACT) Hepatobiliary Subscale (FACT-HBS) and Trial Outcome Index (FACT-TOI), proportion of patients achieving a 25% reduction in opioid use (employing daily morphine equivalence scale) at 30 days and proportion of patients achieving improvement of liver cancer pain/discomfort by ≥ 2 points in pain "intensity at worst" AND with no increase in opioid use (employing daily morphine equivalence scale) on BPI from baseline to 30 days.

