### 7.8.4 Baseline and Change Score Analysis

Descriptive statistics (mean and standard deviation) for FACT-Hep questionnaire scores at baseline will be presented for each subscale and total scores. The same statistics will be generated for change scores from baseline to day 30 and day 90. The comparability of mean baseline scores and change scores at day 30 and day 90 between treatment groups will be assessed using a Wilcoxon rank sum test (**Table 39 and Table 40**).

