### **7.8.5 Proportion of Patients with Clinically Significant Improvement in QOL**

A clinically significant improvement in QOL is defined by  $\geq 5$  points change in the Functional Assessment of Cancer Therapy (FACT) Hepatobiliary Subscale (FACT-HBS) and Trial Outcome Index (FACT-TOI) from baseline. Proportions of patients who had clinically significant improvement in QoL from baseline to day 30 and day 90 are summarized in **Table 41** and compared by a stratified CMH test adjusting for the stratification factor (HCC versus liver metastases) (**Table 41** ).

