**Table 41: Proportion of Patients with Clinically Significant Improvement in QoL**

	RT+BSC N (%)	BSC N (%)	CMH P-value (*)
Patients with QoL at baseline and day 30			
With Clinically significant improvement (**) in QoL	**	**	**
≥5 point change in FACT-HBS	** (**, **)	** (**, **)	0.***
≥5 point change in FACT-TOI	** (**, **)	** (**, **)	0.***
With Clinically significant improvement (**) in QoL	** (**, **)	** (**, **)	0.***
≥5 point change in FACT-HBS	** (**, **)	** (**, **)	0.***
≥5 point change in FACT-TOI	** (**, **)	** (**, **)	0.***
Patients with QoL at baseline and day 90			
With Clinically significant improvement (**) in QoL	**	**	
≥5 point change in FACT-HBS	** (**, **)	** (**, **)	0.***
≥5 point change in FACT-TOI	** (**, **)	** (**, **)	0.***

\* Stratified Cochran-Mantel-Haenszel test adjusting for the stratification factor (HCC versus liver metastases)

\*\* ≥5 point change in both FACT-HBS and FACT-TOI

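### The QoL endpoint counts a FACT-TOI gain of 5 points towards clinically significant improvement, while protocol 2.5 sets 7 points for that scale, and neither document explains the gap

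*Protocol*

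**What the plan says.** The protocol synopsis lists, among the secondary endpoints, the proportion of patients with clinically significant QoL improvement at both follow-up visits, with improvement taken "as defined by a ≥ 5 point change in the Functional Assessment of Cancer Therapy (FACT) Hepatobiliary Subscale (FACT-HBS) and Trial Outcome Index (FACT-TOI"). Protocol 1.2 and 14.1 and SAP 3.2 and 4.2 repeat the definition. SAP 7.8.5 uses the same cut-off: it defines clinically significant improvement by 5 or more "points change in the Functional Assessment of Cancer Therapy (FACT) Hepatobiliary Subscale (FACT-HBS) and Trial Outcome Index (FACT-TOI) from baseline".

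SAP Table 41 has, at each time point, a row labelled as clinically significant improvement, a row for FACT-HBS alone and a row for FACT-TOI alone. A footnote defines the labelled row as "≥5 point change in both FACT-HBS and FACT-TOI".

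Protocol 2.5 explains the choice of instruments and cites a source for the cut-offs. It says that changes in "FACT-G, FACT-HBS, FACT-TOI and FACT-Hep total score by ≥ 6 , ≥ 5 , ≥ 7 and ≥ 8 respectively are considered clinically significant". Read in order, FACT-HBS is 5 and FACT-TOI is 7.

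Protocol 14.2 plans comparisons of clinically significant favourable change on TOI, FACT-Hep and subscales but states no cut-off.

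**The concern.** One scale has two thresholds for the same claim. The figure with a cited basis is 7, and every operative definition uses 5. The HBS value agrees in both places, so the conflict concerns TOI only.

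TOI is the sum of PWB, FWB and HBS, so it contains all of HBS and has a wider range. A 5-point cut-off on TOI is therefore a weaker requirement than the same number on HBS. A reader who knows protocol 2.5 could take a reported TOI responder rate as meeting the standard given there, when some responders gained less than 7 points. At stake is the meaning of a secondary QoL result in a palliative trial, where QoL bears directly on interpretation.

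Protocol 14.2 adds a smaller gap. For FACT-Hep total the only cut-off anywhere is the 8 points in protocol 2.5, and SAP 7.8.5 and Table 41 cover only HBS and TOI.

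**Working it through.** **Thresholds side by side**

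| Place | FACT-HBS | FACT-TOI |
|---|---|---|
| Protocol 2.5 (source cited) | 5 | 7 |
| Protocol synopsis, 1.2, 14.1 | 5 | 5 |
| SAP 3.2, 4.2, 7.8.5, Table 41 | 5 | 5 |
| Protocol 14.2 | none given | none given |

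The 5 cannot be read as applying to HBS only, because Table 41 has a separate TOI row and a footnote naming both scales. Nor does the pilot settle it: protocol 2.4 reports that "25% (95% CI: 10- 47%) of patients had significant improvement in FACT- TOI at 30 days" without saying which cut-off was used.

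**Scale ranges.** With items scored 0 to 4 and the SAP 7.8.1 formulas, PWB has 7 items (maximum 28), FWB 7 (28) and HBS 18 (72), so TOI runs to 28 + 28 + 72 = 128. Five points is 5/72 = 6.9% of the HBS range but 5/128 = 3.9% of the TOI range; 7/128 = 5.5%. A patient who gains exactly 5 on HBS with PWB and FWB unchanged gains exactly 5 on TOI. That patient meets the joint definition at TOI 5 and fails it at TOI 7.

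**Size.** The plan gives no expected rate, power or standard deviation (SD) for this endpoint, so there is no figure to reproduce. All sizes below are illustrations under assumptions: TOI change is normal, SD 8, 12 or 16, mean -5, 0 or +3. Negative means are included because protocol 2.2 says of such patients that "it seems unlikely that QoL in patients with more advanced liver metastases or HCC may improve with no interventions". Patient counts use 21 per arm, that is, the SAP's 42 BPI-evaluable patients split evenly; no QoL-evaluable number is given.

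*TOI-only row.* Rate at cut-off c = 1 - Φ((c - mean)/SD). For mean 0, SD 12: 1 - Φ(5/12) = 33.8% and 1 - Φ(7/12) = 28.0%; the gap is 5.9 points before rounding, or 1.2 of 21.

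| Mean | SD 8: at 5 vs 7 | SD 12 | SD 16 |
|---|---|---|---|
| -5 | 10.6 vs 6.7% | 20.2 vs 15.9% | 26.6 vs 22.7% |
| 0 | 26.6 vs 19.1% | 33.8 vs 28.0% | 37.7 vs 33.1% |
| +3 | 40.1 vs 30.9% | 43.4 vs 36.9% | 45.0 vs 40.1% |

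The gaps run from 3.9 to 9.3 points, or 0.8 to 1.9 patients of 21. A variant treating scores as integers (cut-offs 4.5 and 6.5, SD 10 to 20, mean -5 to +5) gives about 3.5 to 8 points.

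*Anchored to the pilot's 25%.* Choose the mean so that 25% exceed the cut-off. If the pilot used 5, the rate at 7 would be 17.8, 20.0 and 21.2% for SD 8, 12 and 16. If it used 7, the rate at 5 would be 33.6, 30.6 and 29.1%. The gap is 3.8 to 8.6 points either way.

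*Joint row.* Write TOI = HBS + R, with R = PWB + FWB, as bivariate normal. Assume that the HBS SD is 0.60 to 0.75 of the sum of the two SDs, that the correlation of HBS and R is 0.3 to 0.6, and that 18/32 of the mean falls to HBS (by item count). P(HBS ≥ 5, TOI ≥ 5) - P(HBS ≥ 5, TOI ≥ 7) is 1.2 to 3.0 points at mean -5, 1.7 to 3.8 at mean 0 and 1.7 to 3.2 at mean +3. The largest value is 0.038 × 21 = 0.8 of a patient. With an SD share of 0.50 the lowest value is 0.5 points.

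*Between-arm difference.* Let g(m) = Φ((7 - m)/SD) - Φ((5 - m)/SD), the share of an arm gaining 5 to under 7. The arm difference at 5 minus that at 7 is g(RT mean) - g(control mean). Since g is symmetric about 6 and falls away on both sides, a positive shift makes the difference larger at 5 when the midpoint of the two means is below 6, and larger at 7 when it is above.

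- Control -5, shift 8, SD 8 (midpoint -1): 29.6 vs 24.2 points, larger at 5 by 5.4.
- Control 0, shifts 3 to 8: larger at 5 by 0.3 to 2.4 points.
- Control +3, shift 3 or 5: larger at 5 by 0.05 to 0.7 points.
- Control +3, shift 8 (midpoint 7): larger at 7 by 1.1, 0.4 and 0.2 points at SD 8, 12 and 16.

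**The case against.** The strongest reply is that the plan is consistent where it counts. Every operative definition says 5, so what to compute for HBS and TOI is clear. In Table 41 the clinical label belongs to the joint row, where every responder still meets the HBS standard of protocol 2.5, and the TOI-only row states its own cut-off. The cut-off is the same in both arms. A threshold-free analysis is also planned: SAP 7.8.4 says that "change scores at day 30 and day 90 between treatment groups will be assessed using a Wilcoxon rank sum test". The endpoint is secondary and no decision rule depends on it.

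Most of this stands, and it keeps the point modest. It does not remove it. The joint row itself uses TOI at 5. The wording of the synopsis, protocol 14.1 and SAP 7.8.5 can also be read as giving the label to each scale. A Wilcoxon test on change scores does not correct a responder rate described as clinically significant below the protocol's cited value.

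A reader might infer that the lower cut-off favours radiotherapy. The documents do not support that: the sign depends on arm means that they do not give. Protocol 2.2 makes low control means plausible but does not fix them. A reader might also infer that Table 41 labels a TOI gain of 5 as clinically significant by itself; its footnote attaches the label to both scales together.

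**Conclusion.** The inconsistency is real and should be fixed. The operative TOI cut-off is 2 points below the value that protocol 2.5 calls clinically significant, without explanation. Under the stated normal models the joint row is about 1 to 4 points higher than it would be with TOI at 7, under 1 patient of 21. The TOI-only row is about 4 to 9 points higher in each arm, or 1 to 2 patients of 21. These sizes rest on assumed SDs, means, correlations and an even split, none of which the documents supply.

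The HBS rows, the primary endpoint, the sample size and the power are unaffected. Nothing in the documents shows a bias between arms. Nor do they show that 5 was a mistake to be replaced, only that the choice is unexplained.

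**What to change.** Write a dated SAP note before the QoL results are analysed. It should:

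- keep the pre-specified 5-point endpoint, because SAP 2.3 records that this open-label trial has closed accrual and redefinition now would be hard to defend;
- state that the TOI cut-off is below the 7 points in protocol 2.5, with the reason if there is one;
- state which cut-offs apply to the TOI, FACT-Hep and subscale comparisons in protocol 14.2.

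Add two sensitivity rows to Table 41 at day 30 and at day 90: TOI of at least 7 alone, and HBS of at least 5 with TOI of at least 7. Give responder rates by arm and the same stratified CMH test, labelled as sensitivity. In the report, do not describe the TOI rate at 5 points as meeting the protocol 2.5 standard, and say whether the conclusion holds at 7.

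The cost is the note, four table rows with their extra p-values, and slightly lower responder rates in those rows. No new data are needed.

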1.0 OBJECTIVES

1.1 Primary Objective

To determine if patients with symptomatic liver tumours (either HCC or liver metastases) who undergo best supportive care (BSC) plus a single 8 Gy fraction of radiation therapy to the liver experience a significant improvement in symptoms (defined as a ≥ 2 point decrease in their pain “intensity at worst” score on the Brief Pain Inventory (BPI)) from baseline to 30 days as compared to patients receiving BSC alone.

1.2 Secondary Objectives

To compare the two treatment arms with respect to:

- Proportion of patients experiencing grade ≥ 2 adverse events at 30 days and 90 days.
- Proportion of patients alive at 90 days.
- Proportion of patients achieving improvement of liver cancer pain/discomfort by ≥ 2 points from baseline to day 30 and day 90 in all BPI pain scores.
- Proportion of patients reporting clinically significant improvement in QoL from baseline to day 30 and day 90 as defined by a ≥ 5 point change in the Functional Assessment of Cancer Therapy (FACT) Hepatobiliary Subscale (FACT-HBS) and Trial Outcome Index (FACT-TOI).
- Proportion of patients achieving a 25% reduction in opioid use at 30 days (employing daily morphine equivalence).

2.0 BACKGROUND INFORMATION AND RATIONALE

2.1 Liver Cancer

Hepatocellular carcinoma (HCC) is a top cause of cancer-related death globally and the most rapidly increasing cause of cancer death in Canada. In 2013, in Canada, there were over 2000 new HCCs and 1000 deaths due to HCC [*2013 Canadian Cancer Society Statistics*]. HCC is often diagnosed at an advanced stage, and symptoms of pain, anorexia and fatigue are common, especially in patients unsuitable for or refractory to standard local, regional and systemic therapies [*Zhu 2003*].

The liver is a common site for metastases from a variety of gastrointestinal malignancies (e.g. colorectal and pancreatic cancer), as well as non-gastrointestinal malignancies, including, melanoma, breast and gynecological cancers. It is estimated that approximately 25,000 Canadian patients die with liver metastases each year [*2013 Canadian Cancer Society Statistics*]. Surgery and other local therapies are treatment options for the minority of patients with ‘oligo’ or few hepatic confined metastases; however the majority of patients are not suitable for local therapies due to insufficient hepatic reserve and/or a high risk of extra-hepatic disease.

2.2 Symptoms from End-Stage Liver Cancer

The majority of HCC patients experience liver pain or discomfort at some point during their disease course. Pain is likely under-reported in these patients and sometimes dismissed as “discomfort”, despite the significant negative impact on patients’ lives [*Kaiser 2014*]. It has been suggested that there is a need for routine pain assessment as an integral component of advanced HCC patient care [*Kaiser 2014*]. While pain related to liver metastases is not as common as in HCC patients, in later stages, diffuse and/or large hepatic metastases may invade into or stretch the liver capsule causing substantial discomfort. For HCC and liver metastases, the majority of patients become refractory to all therapy for a period of time prior to death and a substantial proportion of these patients suffer from hepatic pain. Effective palliation of hepatic pain can be challenging for these patients and there is a need for improved palliative treatments.

Opioids are commonly used for the palliation of cancer bone pain or other cancer pain outside the liver. However, in patients with impairment of liver function from underlying liver disease, which is common in patients with liver cancer, there is often reduced hepatic blood flow, limiting first pass metabolism, and phase I metabolism (P450 system) and phase II metabolism (glucuronidation) do not work as well. Thus, the parent drug or its metabolites can accumulate, which may precipitate encephalopathy or excessive sedation causing difficulty with compliance and/or in attaining analgesia without toxic side effects. The therapeutic index for opioid-induced pain relief is narrowed in many patients with hepatic pain from liver cancer. Alternate and additional strategies for hepatic pain from end-stage HCC or liver metastases are warranted to reduce pain and improve quality of life (QoL) in these patients.

The natural history of patients with symptomatic liver cancer has not been well researched and there are only a few studies of patient-reported QoL or symptom trials in patients with symptomatic liver cancer. In one study of patients treated with chemotherapy for asymptomatic liver metastases from colorectal carcinoma, there was no improvement in QoL (assessed using EORTC QLQ-C30 and QLQ-LMC21) and more problems with taste, sore mouth, and neuropathy 3 months after chemotherapy [Blazeby 2009]. Although these results are not directly comparable with the HE.1 study cohort who are selected as being unfit for or refractory to systemic agents, it seems unlikely that QoL in patients with more advanced liver metastases or HCC may improve with no interventions or with best supportive care (BSC) alone. There is a paucity of studies that have evaluated the impact of BSC or other treatments on symptoms in patients with end-stage primary or metastatic liver cancer and there is a strong need for prospective evaluation of patient-reported outcomes in such patients treated with novel interventions, such as radiation therapy (RT) or BSC alone.

